### **Material Requirement:**

1. Antimicrobial coating (C16): 100 Liters/ every 3rd week (for each phase)
2. Prepare duplicate Agar plates of
  - a. Chromagar MRSA: Selective media for MRSA (ca. 4000 plates)
  - b. TSA (Tryptic soya agar): for total bacteria count (ca. 4000 plates)
3. Prepare of neutralizing solution: 20 liters
4. Preparation of Polywipe sponge: 2000 (40 boxes)
5. Preparation of buffer solution for dilution (5 liters)
6. Labelling of Agar plates (ca. 8000 plates)
7. Drying of Agar plates at room temperature
8. Autoclave for Sterilization after enumeration

### **Study Status: (Completed)**

#### **Summary**

- Submission of study protocol to ethical review committee: June 2017
- Approval of clinical trials by Research Ethics Committee (Kowloon Central/Kowloon East): Aug 2017

- Completion of background/pilot study: Oct 2017
- Completion of data collection in three phases: June 2018

### Sampling Duration, Time Frame, and work plan:

Background /Pilot Study	Survey	Observation Period (1 st Data Set/Phase 1 )	Washo ut	Survey	Observation Period (2 nd Data Set/ Phase 2)	Wash out	Survey	Observation Period (3 rd Data Set/ Phase 3)
8 weeks	4 weeks	4 weeks	3 week	2 Week	4 weeks	3 week	2 week	4 weeks
04 Sep -30 Oct (2017)	31 Oct – 28 Nov (2017)	01 Dec - 30 Dec (2017)	1st Jan - 05 Feb (2018)		06 Feb – 08 Mar (2018)	26 Mar – 30 Apr (2018)		22 May – 20 Jun (2018)
		8 curtains from Male  12 curtains from Female Cubicle  50% coated curtain, 50% standard curtain			12 Curtains from Male Cubicles  12 Curtains from Female Cubicle  50% coated curtain, 50% standard curtain			16 Curtains from Male Cubicles  16 Curtains from Female Cubicle  50% coated curtain, 50% standard curtain
		No of samples: 480			No of samples: 576			No of samples: 768

## **Brief Summary of Project:**

This project aimed to study the use of the multi-level antimicrobial coating in a working hospital environment. Patient privacy curtains from a public sector hospital were coated and installed in rehabilitation ward in comparison of normally washed curtains in the same setting and compared the mean reduction on both control and treatment end to assess the effectiveness of coating against hospital acquired infections including MDROs.

## **Detailed Description:**

[1] A multi-level antimicrobial coating was produced in the HKUST laboratory using the newly developed staged flow micromixing to prepare contact-killing and anti-adhesion coating made of US-FDA approved polymeric materials. The process was optimized to scale-up the production to 5 liters per hour. 300 liters of the multi-level antimicrobial coating was prepared for the study for a total of 24 weeks as three liters of the coating was needed for one patient privacy curtain.

[2] The study was conducted in the rehabilitation ward of the Kowloon Hospital including both male and female cubicles. It was carried out in three stages with each stage consisting of survey and a four weeks' observation period, separated by three weeks' washout period. In the rehabilitation ward of Kowloon Hospital, a set of male and female cubicle was recruited for the study after getting maximum number of bacterial contamination on patient privacy curtains in pilot study of 8 weeks. Each cubicle had 12 curtains besides admitted patients where all the samples are collected.

[3] Environmental sampling was carried out using sponge swab on the surfaces of the patient privacy curtains. The total bacteria count and quantitative isolation of MRSA was done using established protocols. The total bacteria count provides a quantitative measure of surface cleanliness, while the MRSA count was indicative of the risk of contact transmission from contaminated surfaces. 2-4 weeks survey provided control data on the cleanliness of patients privacy curtains in terms of total bacteria and MRSA counts.

During the study period, the Kowloon Hospital/Queen Elizabeth Hospital infection control team monitored MDROs regularly as part of their routine operation. The procedure and schedule was followed strictly the infection control protocol. All infection control measures implemented after isolation of MDROs were followed according to the hospital's usual practice as advised by the infection control team. In the study, the identification of the organisms in patients more than 48 hours after admission without prior isolation of the organisms in clinical or screening specimens was defined as nosocomial.

[4] The investigators demonstrated a cross-over intervention study. In the first stage of study, half of the patient privacy curtains were considered as treatment (antimicrobial coated) and the other

half of the curtains as control in the same setting in a cubicle. As the study was double blind, so coding was done to identify the treatment as control curtains.

[5] Sample were taken from eight highly touched areas of 50x50 cm^2 on weekly bases for three consecutive weeks on 7th day of first installation. On each period/phase 480, 576 and 786 samples were collected accordingly using the developed sample protocol. In total, the investigators collected 1824 samples from 76 patient privacy curtains in which 912 (50%) were control curtain and 912 (50%) are antimicrobial coated curtains.

[6] Healthcare workers from the participating wards were assessed for their acceptance of the multilevel antimicrobial disinfectant coating by way of a questionnaire. Additional reformulation may be necessary to increase the acceptability of the coating technology to the healthcare workers.

[7] For the bacteria count, duplicate plates of TSA (total bacteria count) and Chromagar MRSA (selective agar for MRSA detection) were used for enumeration. CFU/m^2 is calculated after 48 hours' incubation at 37C. Data was analyzed using SPSS V.21 to assess the effectiveness of the coating in reducing the contamination level of the surface. The total bacteria count on the patient privacy curtains was compared between the control and treatment group using Mann-Whitney test and T-test. ANOVA analysis allowed the comparison of different periods of study of phase wise as well as week wise. The significance of the statistical test is defined to have a P value <0.05.

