## **Study Objectives**

1) To compare the antibacterial effect of in use antimicrobial coated patient privacy curtains with standard curtains:

- i) Total bacterial count over time
- ii) Time of first MDRO contamination
- iii) Percentage of MDRO contamination

2) To assess healthcare worker's acceptance of the multi-level antimicrobial coating.

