## **Primary Outcome Measure:**

1. Change in total bacteria count and MRSA in control vs treatment patient privacy curtains

To quantify the effectiveness of antimicrobial coating, percentage change (both in log and linear scale) in mean bacterial count (CFU/m^2 units) in control versus treatment curtains is used. The data was collected in 3 phases of 4 weeks each, so the time frame used is representative of the complete observation period.

[Time Frame: 12 weeks]

2. Durability of antimicrobial coating in affecting bacterial load amongst treated patient privacy curtains

Change in bacterial load amongst treatment curtains is observed as a function of time during each phase of the data collection period (for 4 weeks). In total, data was collected in 3 phases of 4 weeks each, so the total observation period is 12 weeks and timeframe of each frame is 4 weeks.

3) [Time Frame: 12 weeks]

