**Environmental Sampling:**

1. Sampling Frequency: Curtains were sampled on a weekly basis for the total duration of 3 weeks. So, every curtain was sampled three times during complete sampling duration. First 7 days was the time of exposure to contaminate leading with next 3 weeks of sampling.
2. Sampling Area: Each curtain was sampled for eight areas for the size of 50x50cm^2 each. Four areas from top side starting from patient’s head side to toe side on the bed, and four areas from bottom side moving from toe to head side. As the size of curtain varies from 430cm to 480cm in length, for the best results after pilot study, we calibrated 8 areas keeping 50 cm from above, 37cm from lateral margins and 57-70cm in between.

- Area 1: Upper Head side
- Area 2: Upper 2nd area
- Area 3: Upper 3rd area
- Area 4: Upper Toe Area

- Area 5: Lower Toe Side
- Area 6: Lower 2nd area
- Area 7: Lower 3rd area
- Area 8: Lower Head Area

[figure not shown]

Fig 3. Illustration of 8 sampling location on a curtain received from Rehabilitation ward of KH, Designated 50x50cm^2 area were sampled following the protocol

3. Sampling Side of the curtain: Sampling was done from the inner side of the curtain, (inner side was more exposed to the risk of contamination as a frequent touch of the patient on the bed, nursing staff, cleaning staff, monitoring staff, attendants, and doctor).
4. Sampling material: Polywipe sponge were used to sample 50x50cm^2 area on the curtain.
5. Sampling technique: Both sides of a sponge were used by swabbing on the curtain. Holding the sponge from the middle of one side with the right hand, keeping vertically, swab area starting from upper left margin towards the upper right margin of 50x50cm^2 area from one side of the sponge. The same method was used swabbing from right to left side with other side of the sponge. Sampling was done gently, slowly and softly by not repeating the swab to sampled area.
6. Sampling frame: 50x50cm^2 frame of plastic covered with a disposable plastic sheet was used as back support for smooth sampling and accurate measurement. Every time, sterilized plastic was removed and new sheet was used to reduce the chance of microbial spread or false positive result on control and treatment arm of the study

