### **Data Analysis:**

The duplicate system in total bacteria count helped to monitor the validity of the data point. Logical elimination of plate count was determined while comparing the bacteria morphology of the first plate with the second plate. If the bacteria morphology was not consistent, the plate with more bacteria was eliminated, and the plate with a lower value was taken due to the chance of contamination on a non-selective agar plate.

The Colony Forming Unit (CFU) obtained on the duplicated plates was averaged, and the CFU per unit area was calculated. CFU per unit area was allowing the comparison of microbiological contamination of the sampled surface. With the dilution factor of the samples, the Total bacteria count (TBC) was determined. The microbiological contamination level of an item was represented by the CFU/unit area of the item.

CFU on Müller-Hinton Agar represents the total aerobic bacteria count. By dividing the CFU with the area sampled, CFU/m^2 was obtained. Data points that did not contain any CFU count were assumed to have 0.5 CFU. The assumption was made based on the minimum detection value that can be obtained.

All analysis was carried out using Statistical Package for the Social Sciences for Windows, version 25.0 (SPSS, Inc., Chicago, IL, USA) to analyze the effectiveness of the coating in reducing the contamination level of the surface. The total bacteria count on the patient partition curtains was compared to the control and treatment group using Mann-Whitney test and T-test. Chi-square test and Fisher's exact test were also used to compare categorical variables such as the percentage of MRSA. Parametric test was carried out to evaluate the cleanliness baseline in each of the wards before and after treatment. ANOVA analysis allowed the comparison of different periods of study and the differences among wards. Median time to first contamination (days) of MDRO for each curtain type was compared using the Wilcoxon rank-sum test. The significance of the statistical test was defined to have a P value <0.05.

Healthcare workers from the participating wards were assessed for their acceptance of the multilevel antimicrobial disinfectant coating by way of a questionnaire. Additional reformulation may be necessary to increase the acceptability of the coating technology to the healthcare workers.

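### The week-wise ANOVA is named without any within-curtain term although every curtain supplies all three weeks; read as an ordinary ANOVA on swabs, its error rate is right only by coincidence

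*Combined protocol and SAP*

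**What the plan says.** Week comparison (Detailed Description, item 7): "ANOVA analysis allowed the comparison of different periods of study of phase wise as well as week wise". One unqualified method serves both phases and weeks. The Data Analysis section gives a parallel sentence, "ANOVA analysis allowed the comparison of different periods of study and the differences among wards", which does not mention weeks.

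Sampling (Environmental Sampling, items 1 and 2): "So, every curtain was sampled three times during complete sampling duration", and "Each curtain was sampled for eight areas for the size of" 50x50 cm² each. The Detailed Description gives the total: "In total, the investigators collected 1824 samples from 76 patient privacy curtains", half of the samples in each arm.

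Questions about time: Study Objectives lists "Total bacterial count over time" as item 1(i), a comparison of coated with standard curtains. Primary Outcome Measure 2 (durability) says "Change in bacterial load amongst treatment curtains is observed as a function of time during each phase of the data collection period" and assigns no test.

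The other tests named for bacterial counts (Mann-Whitney, t-test) carry no pairing or clustering, and the sample size section treats specimens as two independent groups.

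**The concern.** Phases are counted as separate sets of curtains (20 + 24 + 32 = 76 in the work plan), so a comparison of phases is a comparison between curtains. Weeks are not separate sets: the same curtains return at each visit. An ordinary ANOVA on swabs then makes two mistakes that pull in opposite directions. It leaves stable differences between curtains in the error term, although they cancel when weeks are compared. It also ignores any fluctuation that the eight swabs of one curtain share at one visit.

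The week-wise ANOVA is the only named test that compares weeks, and change over weeks is what primary outcome 2 is about. If the test is too conservative, a non-significant week effect could be taken as a sign of a durable coating. If it is too liberal, a chance difference between visits could be reported as loss of effect.

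The problem is separate from clustering in the coated-versus-control tests. Averaging each curtain over its 3 × 8 = 24 swabs would repair those tests, but it removes week altogether.

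**Working it through.** **1. The plan's own figure.** With d = 0.20, one-sided alpha 0.05 and power 0.95, the noncentrality at 542 per group is 0.20 × √(542/2) = 3.292 and the power is 0.9501. The 542 per group (1084 in total) reproduces. It concerns the arms and assumes independent specimens; no figure is given for the week comparison.

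**2. Structure.** 76 curtains × 3 visits × 8 areas = 1824, the stated total. Per arm, 912 / 24 = 38 curtains. Half of 20, 24 and 32 gives 10, 12 and 16 coated curtains per phase.

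**3. Error terms.** Write the log count as week + curtain (variance c) + curtain-by-week (variance w) + swab error (variance e).

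- With no week effect, the week mean square has expectation e + 8w.
- The ordinary ANOVA divides by an error mean square of about e + w + c.
- These agree when c = 7w, which includes the case of both being zero. If c > 7w the test is conservative; if c < 7w it is liberal.
- A repeated-measures test divides by the curtain-by-week mean square, whose expectation is e + 8w, so it is correct throughout.

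**4. Size.** Assumptions: 38 distinct coated curtains, all phases pooled, total variance 1 (the plan's SD of 1 log). The splits are my assumptions; the documents give none. Simulation used 40,000 runs per row. The hand check is exp(−3.0/(e + 8w)), which follows because the 5% critical value of F on 2 and 909 df is about 3.0 and the upper tail is then close to exp(−F). Power is for an assumed drift of 0, 0.1, 0.2 log over the three visits.

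| c / w | e + 8w | Hand check | Type I, ordinary | Type I, repeated | Power, ordinary vs repeated |
|---|---|---|---|---|---|
| 0.5 / 0 | 0.50 | 0.2% | 0.4% | 4.8% | 57% vs 87% |
| 0.3 / 0 | 0.70 | 1.4% | 1.5% | 5.2% | 58% vs 74% |
| 0.1 / 0 | 0.90 | 3.6% | 3.7% | 4.9% | 58% vs 62% |
| 0.35 / 0.05 | 1.00 | 5.0% | 5.2% | 4.8% | 59% vs 57% |
| 0.3 / 0.05 | 1.05 | 5.7% | 6.1% | 5.0% | 59% vs 55% |
| 0.1 / 0.1 | 1.60 | 15% | 15.7% | 5.0% | 62% vs 38% |
| 0.1 / 0.2 | 2.30 | 27% | 27.7% | 5.1% | 64% vs 28% |

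In the last two rows the higher power of the ordinary test only reflects its inflated error rate.

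**5. Per phase.** Durability is defined within each phase. The squared deviations of (0, 0.1, 0.2) from their mean sum to 0.02, so for n coated curtains the repeated-measures noncentrality is n × 8 × 0.02 / (e + 8w). At 0.3 / 0 this is 2.29, 2.74 and 3.66 for n = 10, 12 and 16, giving power of about 22%, 26% and 35%.

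**6. Arm-by-week.** With 38 curtains per arm, drift only in the coated arm and the split 0.3 / 0, the noncentrality is half that of the pooled single-arm test: (38 × 8 × 0.02 / 0.7) / 2 = 8.69 / 2 = 4.34. On 2 and 148 df the power is about 44%.

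**The case against.** The text never says one-way, and a repeated-measures ANOVA is also an ANOVA. A reader might infer that the plan prescribes the wrong test; strictly, it leaves the error term unspecified. That stands. But the surrounding methods are all independent-sample tests and the sample size counts specimens, so the ordinary ANOVA is the natural reading, and the wording needs changing either way.

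A reader might also infer that the week-wise ANOVA is the designated test for durability and for objective 1(i). The documents do not support this. Primary outcome 2 has no test assigned, and objective 1(i) compares the arms, for which Mann-Whitney and the t-test are named. What holds is narrower: no other named test compares weeks. Nor does the Data Analysis section repeat the week comparison; its ANOVA covers periods and wards.

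The strongest objection concerns power. The gain from repeated measures appears only when curtain-by-week variance is close to zero. With as little as 0.05 beside a curtain variance of 0.3, the ordinary test has near-nominal error (about 6%) and the power advantage is gone (59% vs 55%). The pooled powers also do not describe a per-phase endpoint. So it cannot be said that this trial lost power. The case for the change rests on a valid error rate.

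Finally, a within-curtain term alone would not answer the durability question. In coated curtains a rise over weeks may be ordinary build-up of contamination, and a curtain effect does not absorb a ward-wide shift at one visit. This is correct, and the fix therefore uses both arms.

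**Conclusion.** The concern holds in this form: weeks are compared with an unqualified ANOVA, no within-curtain term is named anywhere, and the sampling scheme makes week a within-curtain factor. That structure is documented. The reading as an ordinary ANOVA on swabs is an inference from the context, though a strong one.

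The direction and size of the error in this trial are unknown, because they depend on variance components that the documents do not give. Over the assumed splits, the error rate runs from about 0.4% through about 6% to about 16% and 27 to 28%, against about 5% with repeated measures. A non-significant week effect would be weak evidence of durability under either analysis, since per-phase power for a 0.2 log drift is only about 22% to 35% at 0.3 / 0. The plan should be changed; confidence is moderate.

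**What to change.** In the Detailed Description, item 7, replace the week-wise ANOVA with wording such as: *Weeks are compared within curtain. The mean log count of the eight areas per curtain and visit is analysed in a mixed model using both arms, with curtain as random subject and arm, week, arm-by-week, phase and cubicle as fixed effects. Durability is judged by the arm-by-week term, reported with week-specific estimates and confidence intervals. A non-significant week or arm-by-week effect is not taken as proof of durability. Phases are compared against curtain-to-curtain variance.*

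Align the ANOVA sentence in the Data Analysis section, and link primary outcome 2 explicitly to this model. The concurrent controls remove build-up and ward-wide shifts as far as both arms share them. State how many curtains were replaced during a phase and how they were handled; each curtain's available visits can stay in the model.

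The cost is rewording and a modest re-analysis of data already collected, with no new samples. The price is wider confidence intervals if visits fluctuate, and limited power for the interaction (about 44% even pooled, in the case worked above), which is why estimates and intervals should carry the conclusion.

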## **Study Design:**

Interventional cross-over study

## **Study Objectives**

1) To compare the antibacterial effect of in use antimicrobial coated patient privacy curtains with standard curtains:

- i) Total bacterial count over time
- ii) Time of first MDRO contamination
- iii) Percentage of MDRO contamination

2) To assess healthcare worker's acceptance of the multi-level antimicrobial coating.

## **Inclusion Criteria**

For the clinical setting of the allocated ward with a prior history of high MDRO (preferably MRSA) prevalence is included.

## **Exclusion Criteria**

For the clinical setting of the allocated ward with a prior history of low MDRO prevalence is excluded.

## **Primary Outcome Measure:**

1. Change in total bacteria count and MRSA in control vs treatment patient privacy curtains

To quantify the effectiveness of antimicrobial coating, percentage change (both in log and linear scale) in mean bacterial count (CFU/m^2 units) in control versus treatment curtains is used. The data was collected in 3 phases of 4 weeks each, so the time frame used is representative of the complete observation period.

[Time Frame: 12 weeks]

2. Durability of antimicrobial coating in affecting bacterial load amongst treated patient privacy curtains

Change in bacterial load amongst treatment curtains is observed as a function of time during each phase of the data collection period (for 4 weeks). In total, data was collected in 3 phases of 4 weeks each, so the total observation period is 12 weeks and timeframe of each frame is 4 weeks.

3) [Time Frame: 12 weeks]

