### Sample size calculation using G-power 3.1.9.2

In our previous study carried out in orthopedics wards, a total of 2249 samples were taken from hospital surfaces over a study period of 1 year. The following was the mean and standard deviation of log total-bacteria-count in the previous study.

Group Statistics					
Type (1/2)		N	Mean	Std. Deviation	Std. Error Mean
log (CFU/m  )	treatment	1130	4.13126	.544325	.016193
	control	1119	4.32627	.531846	.015899

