### Basic information of previous field study in orthopedic ward

#### Assumptions:

1. The sample taken may have a higher standard deviation than the previous study. SD assumed to be 1log.
2. 0.21 log reduction on the total bacteria count on the bed partition curtains was assumed. This was based on the difference of the control and the treatment group in the previous study.

t tests - Means: Difference between two independent means (two groups)

Analysis: A priori: Compute required sample size

Input: Tail(s) = One  
 Effect size d = 0.2000000  
 α err prob = 0.05

	Power (1- $\beta$ err prob)	=	0.95
	Allocation ratio N2/N1	=	1
Output:	Noncentrality parameter $\delta$	=	3.2924155
	Critical t	=	1.6462631
	Df	=	1082
	Sample size group 1	=	542
	Sample size group 2	=	542
	Total sample size	=	1084
	Actual power	=	0.9500669

Hence a minimum of 1084 specimens were adequate for our study. To best fit the wards size and sampling schedule, we reckon a sample size of 1800 was best suited for our study.

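### Primary outcome 1 uses an undefined log-scale percentage change; define it as a log reduction, with inference that treats the curtain as the unit

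*Combined protocol and SAP*

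**What the plan says.** Primary Outcome Measure 1 covers two counts: "Change in total bacteria count and MRSA in control vs treatment patient privacy curtains". Its effect measure is worded: "To quantify the effectiveness of antimicrobial coating, percentage change (both in log and linear scale) in mean bacterial count". The same sentence sets the unit at CFU/m². No formula is given there or in Data Analysis, and the log base is not stated.

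The sample size section works on the log scale. It introduces its table with "The following was the mean and standard deviation of log total-bacteria-count in the previous study" and states the planning effect as a log reduction: "0.21 log reduction on the total bacteria count on the bed partition curtains was assumed". The calculation is one-sided ("Input: Tail(s) = One"), and its result is a number of specimens.

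On the sampling structure, Environmental Sampling says "Each curtain was sampled for eight areas" and "So, every curtain was sampled three times during complete sampling duration". Detailed Description [5] gives the total: "In total, the investigators collected 1824 samples from 76 patient privacy curtains", half of the samples in each arm. Curtain installation says that coated and uncoated curtains hung alternately within each cubicle, and the caption of Fig 2 describes this as matched pairs.

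Data Analysis compares total count by Mann-Whitney test and t-test, and percentage MRSA by chi-square and Fisher's exact tests, at P<0.05. It does not state the unit of analysis, the scale of the t-test, the sidedness or which test decides. Zero counts are set to 0.5 CFU.

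**The concern.** A mean log count has no natural zero. Dividing a log difference by a mean log therefore gives a percentage that depends on where the log scale happens to start: on the area unit, and on how contaminated the control curtains are. One of the two stated primary effect figures could then look trivial while the other, from the same data, looks substantial. A reader could not compare the log-scale figure across phases, organisms or studies.

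The second issue is separate but bears on the same estimate. Any replacement measure needs a confidence interval and a test. The curtain is what was coated or left uncoated, and its samples share one fabric, one bed space and one coating process. If they are counted as independent, the interval is too narrow and the test rejects too often.

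**Working it through.** **Plan's own figure.** Inputs from the sample size section: d = 0.20, one-sided alpha 0.05, power 0.95. The normal formula gives 2 × (1.645 + 1.645)² / 0.20² ≈ 541 per group. The exact noncentral t calculation gives 542 per group, 1084 in total, with power 0.9501. This matches the plan, with the specimen as the unit.

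**Log-scale percentage.** The previous-study mean log CFU/m² is 4.32627 for control and 4.13126 for treatment (base 10 assumed).

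- Difference: 4.32627 − 4.13126 = 0.19501.
- Literal percentage: 0.19501 / 4.32627 = 4.5%.
- Geometric-mean reduction: 1 − 10^(−0.19501) = 36.2%.
- Unit: per 50 × 50 cm area (0.25 m²) both means fall by 0.60206, so the literal figure becomes 0.19501 / 3.72421 = 5.2%. The 36.2% does not move.
- Baseline, keeping CFU/m²: the Results section reports an average of 50 to 250 colonies per TSA plate. With a 10 ml bag, 0.1 ml plated, a 1:10 dilution and 0.25 m², one colony is 4000 CFU/m², so these plates correspond to 5.30 to 6.00 log. A 0.20 log reduction then reads as 0.20/5.30 = 3.8% to 0.20/6.00 = 3.3%, although it is a 36.9% lower geometric mean in both cases.

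**Clustering.** 8 areas × 3 weeks = 24 samples per curtain, and 1824/76 = 24. That is 38 curtains and 912 samples per arm. The intracurtain correlation (ICC) is not in the documents; 0.02, 0.05 and 0.10 are assumptions.

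- Design effect: 1 + 23 × ICC = 1.46, 2.15, 3.30.
- Two-sided null error of a sample-level test: 2 × [1 − Φ(1.96/√DE)] = 10.5%, 18.1%, 28.1%. A simulation of 20,000 datasets gave 10.6%, 18.1% and 27.9%. A t-test on curtain means gave 5.2%, 4.9% and 4.7%.

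**Curtain-level interval around 36.2%.** SE = SD × √(2/912 × DE), with t on 74 degrees of freedom (1.99). Two SDs are shown: about 0.538, pooled from the previous study (0.544 and 0.532), and the planning value of 1 log.

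| Assumed ICC | SD 0.538 | SD 1 |
|---|---|---|
| 0 | 28.4% to 43.1% | 20.9% to 48.5% |
| 0.05 | 24.4% to 46.1% | 12.5% to 53.4% |
| 0.10 | 21.3% to 48.3% | 5.7% to 56.8% |

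**MRSA and zeros.** Assume for illustration that 20% of control and 10% of coated samples are positive, each at 10 colonies. The difference in mean log is 0.10 × log10(10/z), where z is the value given to zeros. At z = 0.5 it is 0.130, a 25.9% reduction; at z = 0.05 it is 0.230, a 41.1% reduction. Duplicate plates are averaged, so the smallest positive result is (1 + 0)/2 = 0.5 colony. A substitute above 0.5 would rank an empty sample above a positive one.

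**The case against.** The strongest reply is that the unit is not open. The outcome sentence fixes CFU/m², and the rest of the document keeps to it. A reader might infer that the trial's figure is indeterminate, pointing out that the same means expressed per cm² would give 0.19501/0.32627 = 59.8%. The documents do not support that: nobody planned a per-cm² analysis, and in the stated unit the literal figure is determinate. What stands is that its size does not measure the coating effect.

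A second reply is that a log reduction was meant. The sample size section uses that term, so this is plausible, and on that reading a clarification is enough. The outcome definition does not say so, however. The linear-scale percentage is valid either way, and a hypothesis test on log counts is unaffected by the area unit.

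Third, clustering is a different question from the log percentage, and its size rests on ICCs the documents do not give. Both points are fair. A reader might infer that the trial's P values are inflated by a known amount; the documents do not support that, because they do not state the unit of analysis. The structural fact remains: 24 samples per curtain, and no stated allowance for it.

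Finally, the unnamed deciding test could be read as a serious multiplicity problem. Under an independent lognormal null, two-sided, accepting either the log t-test or Mann-Whitney gives 6.2%, and 8.2% if the t-test uses linear counts. That is a lesser matter.

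**Conclusion.** The point holds in two parts. First, the log-scale percentage change is undefined and, read literally, uninformative about the coating effect: 4.5% against a 36.2% lower geometric mean from the same 0.195 log difference. This assumes base-10 logs and borrows means from an earlier orthopaedic-ward study, so it illustrates the measure and does not predict this trial's result.

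Second, the estimate needs curtain-level inference. Treating samples as independent would give two-sided null error of about 10.5% to 28% over assumed ICCs of 0.02 to 0.10. How far the interval widens depends on both the ICC and the SD, and the planning SD of 1 log gives the pessimistic end.

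For MRSA, a log reduction removes the dependence on area unit but remains sensitive to the value given to zeros when most samples are zero. It should not lead there. This is a correction that should be made, not a flaw that invalidates the study.

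**What to change.** **Total count.** Replace the log-scale percentage with the coated-minus-control difference in mean log10 CFU/m², stating the base. Back-transform it as 100 × (1 − 10^difference). Give a 95% CI and a deciding test that treat the curtain as the unit, through curtain means or a curtain random effect. Adjust for phase and cubicle, and for the adjacent coated/uncoated pairs if they can be identified from the codes. State whether the test is one- or two-sided. Report the linear percentage and the Mann-Whitney test as supportive.

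**MRSA.** Lead with percentage positive, in an analysis that allows for curtain. Report the log reduction as supportive, under several substitutions for zeros no larger than the smallest positive averaged count, and state whether substitution comes before or after conversion to area.

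**Disclosure.** Study Status records that data collection finished in June 2018, so say that these choices were made afterwards.

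**Cost.** Revised outcome and analysis wording, one reanalysis of existing data and a disclosure sentence; no new data. Intervals will be wider than sample-level ones if counts correlate within curtains, and the linear-scale percentage loses equal standing.
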